## Datasets for analyses

All statistical analyses will be conducted on an intention-to-treat basis, with patients analyses according to their assigned treatment arms (Figure 1). No or minimal losses to follow-up for the primary and secondary outcomes are anticipated. Complete – case analysis will be carried out for all the outcomes. However, if more than 5% of missing data were found for the primary outcome, a sensitivity analysis using multiple imputations and estimating – equation methods will be carried out.

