### *Intent-to-treat population (ITT):*

The intention-to-treat (ITT) population is defined as all randomized patients. Patients in this population will be analyzed in the arm allocated by randomization, regardless of eligibility criteria and treatment received, drop out, or switched treatments during the trial.

The modified intention-to-treat (m-ITT) population will exclude participants whose surgical procedure was canceled, who did not meet the eligibility after randomization, who withdraw consent and without evaluable efficacy endpoints.

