### *As-treated:*

The as-treated population is defined based on the treatment they actually received during the trial. This takes into account the deviations from the

assigned treatment regimen, aka.the cross-overs from the assigned treatment to the other treatment.

Per-protocol population (PP):

The per-protocol (PP) population includes all patients randomized to their randomization arm and without major protocol deviations. In particular, the analysis will be restricted to patients finished the full-term intervention as assigned. Participants with treatment interruptions, or early discontinuations of NO inhalation will be excluded from PP analysis. A list of exclusion will be validated by the steering committee before freezing the database.

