## **Sensitivity Analysis**

The pre-specified sensitivity analysis will re-estimate the iNO effect on the primary outcome using GLM using a binomial distribution. Additional adjustment will be made for subgroups and any variables showing substantial imbalance across treatment arms at baseline. We assessed the balance of randomised groups on baseline and procedural characteristics using absolute standardised difference, defined as the absolute difference in means, mean ranks, or proportions divided by the pooled standard deviation. Baseline and procedural characteristics with absolute standardised difference  $>0.15$  ( $1.96 * \sqrt{1/330 + 1/330}$ ) were considered to be imbalanced and would be adjusted. The other way of exploring the potential imbalance across treatment arms will be achieved by constructing a logistic regression model to estimate the treatment effect and predictors of PPCs. Collinearity and overfitting will be assessed through Pearson's correlation tests and variation inflation factors. If outcome events are observed to be rare, a Poisson regression will be employed. Classic logistic regression will be performed with a consistent number of events, and the number of covariates in the model will be decided based on the number of outcomes. The ARISCAT score and operation duration score used as one randomization stratification will be treated as continuous variables, exploring their continuous impacts on the outcome.

Time-to-event (PPC) within the observation window (7 days and 30 days respectively) will be assessed using Kaplan-Meier curves and compared with log-rank tests. Per-protocol and as-treated analyses of PPCs will serve as sensitivity analyses. If a low missing rate (< 5%) in the primary outcome were presented, an extra sensitivity analyses with multiple imputations would be performed.

In addition to the standard analysis described above, the following analyses will be performed to test the robustness of the trial findings:

- (1) the count of positive component events within the composite will be assessed and groups will be compared using a Wilcoxon rank-sum test, and odds ratio with the 95% confidence interval will be assessed with a proportional odds logistic regression;
- (2) the effect of inhaled NO on each component will be analyzed using a GLM using Bonferroni correction for multiple comparisons with 99.37% Bonferroni-corrected confidence intervals reported ( $1 - 0.05/8 = 0.9937$ );

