## **Safety Outcome Analysis**

Incidence of safety outcomes will be compared as primary analysis. The count of NO concentration adjustments will be modeled using Poisson regression.

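### Safety outcomes are compared only by assigned arm in all randomised patients, so any cross-over between gases pulls a harm of NO towards zero; the as-treated set the SAP already defines is not used for safety (minor)

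*SAP*

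**What the plan says.** - *Datasets for analyses* sets one basis for everything: "All statistical analyses will be conducted on an intention-to-treat basis, with patients analyses according to their assigned treatment arms". It makes no exception for safety. *Baseline and intraoperative Characteristics* repeats the ITT rule for all analyses.
- *Intent-to-treat population* gives the definition: "The intention-to-treat (ITT) population is defined as all randomized patients". Patients stay in their allocated arm "regardless of eligibility criteria and treatment received, drop out, or switched treatments during the trial".
- *Safety Outcome Analysis* says "Incidence of safety outcomes will be compared as primary analysis" and names no other population.
- *As-treated* provides a second grouping: "The as-treated population is defined based on the treatment they actually received during the trial". It exists to handle "the cross-overs from the assigned treatment to the other treatment".
- *Sensitivity Analysis* gives that set its only use: "Per-protocol and as-treated analyses of PPCs will serve as sensitivity analyses".
- The modified ITT set "will exclude participants whose surgical procedure was canceled", so randomised patients without an operation are foreseen. No analysis is assigned to this set. It also requires evaluable efficacy endpoints, so it is not a safety set.

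No safety population is defined anywhere in the SAP.

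**The concern.** Under ITT, a patient allocated to NO but given placebo counts in the NO column, and the reverse. For an efficacy claim this works against the claim, which is why ITT is the cautious choice there. For harm it works the other way, because the arms look more alike than the two gases are. The SAP recognises departures from assignment and has a received-treatment set to examine them, but applies it to benefit and not to harm.

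Patients who received no gas raise a separate problem. One of the listed safety outcomes is the number of NO concentration adjustments, to be modelled by Poisson regression. For such a patient this count is either zero by construction or undefined, and the SAP does not say which.

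At stake is a modest understatement of the excess risk at 80 ppm NO, and a safety denominator that is not clearly fixed.

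**Working it through.** The SAP states no figure on this point, so there is nothing to reproduce. It gives no safety event rate, cross-over rate or non-exposure rate. The rates below are assumptions. Only the 330 per group comes from the SAP (*Sample Size Consideration*).

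**Cross-over.** Let pt and pc be the true event risks on NO and on placebo, u the share of the NO arm given placebo, and x the share of the placebo arm given NO. Assume that risk depends only on the gas received.

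- ITT rate, NO arm: (1 − u)·pt + u·pc
- ITT rate, placebo arm: (1 − x)·pc + x·pt
- ITT risk difference: (1 − u − x)·(pt − pc)

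**No gas.** If a share c of each arm received no gas and is counted as event-free, both rates are multiplied by (1 − c). The risk difference shrinks by (1 − c) and the risk ratio does not change.

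Results for pt = 10% and pc = 5%, with power for a two-sided 5% test at 330 per arm (normal approximation, no continuity correction):

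| Scenario | ITT rates, NO vs placebo | Risk difference (points) | Risk ratio | Power |
|---|---|---|---|---|
| All receive assigned gas | 10% vs 5% | 5.0 | 2.00 | 68.5% |
| u = 2%, x = 0 | 9.9% vs 5% | 4.9 | 1.98 | 67.0% |
| u = x = 5% | 9.75% vs 5.25% | 4.5 | 1.86 | 59.3% |
| u = x = 10% | 9.5% vs 5.5% | 4.0 | 1.73 | 49.6% |
| c = 5% in each arm, event-free | 9.5% vs 4.75% | 4.75 | 2.00 | 66.0% |

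Example, third row: 0.95 × 10 + 0.05 × 5 = 9.75; 0.95 × 5 + 0.05 × 10 = 5.25; 9.75 − 5.25 = 4.5 = 0.90 × 5.0.

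The factor does not depend on the assumed risks. With 5% cross-over in each arm, 20% versus 10% gives 9.0 points instead of 10.0 (power 90.1% instead of 95.1%), and 6% versus 2% gives 3.6 instead of 4.0 (power 65.6% instead of 74.7%).

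**Which rule applies to patients with no gas?** *Datasets for analyses* prescribes complete-case analysis for every outcome. A patient whose operation was cancelled has no intraoperative record and could be treated as missing, in which case the last row of the table does not arise. Or the patient could be entered as having no event. The text settles neither. Cross-over dilution remains under both.

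**The case against.** The strongest reply is that the dilution is likely to be small. The abstract places randomisation after induction of anaesthesia, *Randomization and Masking* keeps the allocation closed until the morning of surgery, and *Intervention* starts the gas directly after intubation. That leaves little room for a patient to be randomised and not exposed. At 2% one-sided cross-over the loss is 0.1 points on an assumed 5.0. This stands, and it is why the point is minor. It does not remove the point, because the SAP itself foresees both cancelled surgery and cross-over.

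Three stronger readings are tempting, and the SAP does not support them.

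- A reader might infer that the safety events can arise only with study gas. Hypotension, arrhythmia, high airway pressure and major bleeding can occur in any anaesthetised surgical patient. Only harm caused by NO, and the count of NO adjustments, require exposure.
- A reader might take the 10% in *Sample Size Consideration* as the share never exposed. It is an allowance for dropouts, and *Datasets for analyses* expects few or no losses for the primary and secondary outcomes.
- A reader might infer that cancelled patients certainly dilute the result. They may drop out under the complete-case rule, and if they are counted as event-free in balanced numbers the risk ratio is unaffected.

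It can also be said that grouping by gas received gives up the protection of randomisation, particularly if the reason for a switch is related to risk. That stands too, and it is the reason to keep the ITT table.

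**Conclusion.** The point holds as a minor one. The SAP compares safety only by assigned arm in all randomised patients, and leaves its own as-treated set unused where ITT is not the cautious choice. Cross-over shrinks the risk difference by (1 − u − x): 2% with 2% one-sided cross-over, 10% with 5% in each arm, 20% with 10% in each arm. This assumes that risk follows the gas received and that switching is unrelated to risk. The actual size cannot be found from the SAP, and it is close to nil if nearly everyone receives the assigned gas. The handling of patients who received no gas is unspecified. The SAP gives no ground for saying that a harm of NO would be substantially hidden.

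**What to change.** In *Safety Outcome Analysis*, and for the adverse reactions in *Secondary Analysis*, state that safety is analysed in all patients who received any study gas, grouped by the gas actually received, with the ITT version reported alongside. Say in the same place how a patient who received both gases is grouped, and whether, in the ITT version, a patient who received no gas counts as event-free or as missing. Report the numbers crossed over and never exposed by arm, so that readers can judge how far the two versions could differ.

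The cost is a sentence or two in the SAP and a second run of the safety tables. The as-treated grouping is already defined. The downside is that the as-treated comparison is not strictly randomised, so it should be read next to the ITT result and not in place of it.

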### *Intent-to-treat population (ITT):*

The intention-to-treat (ITT) population is defined as all randomized patients. Patients in this population will be analyzed in the arm allocated by randomization, regardless of eligibility criteria and treatment received, drop out, or switched treatments during the trial.

The modified intention-to-treat (m-ITT) population will exclude participants whose surgical procedure was canceled, who did not meet the eligibility after randomization, who withdraw consent and without evaluable efficacy endpoints.

### *As-treated:*

The as-treated population is defined based on the treatment they actually received during the trial. This takes into account the deviations from the

assigned treatment regimen, aka.the cross-overs from the assigned treatment to the other treatment.

Per-protocol population (PP):

The per-protocol (PP) population includes all patients randomized to their randomization arm and without major protocol deviations. In particular, the analysis will be restricted to patients finished the full-term intervention as assigned. Participants with treatment interruptions, or early discontinuations of NO inhalation will be excluded from PP analysis. A list of exclusion will be validated by the steering committee before freezing the database.

### **Stopping rules**

The patient's participation in the study is terminated if the patient (or trusted person) withdraws consent. In the event that the investigator temporarily or permanently discontinues participation in the study for any reason that would be in the best interest of the patient, particularly in the case of serious adverse events suspected to be related to the intervention strategy being tested, the patient remains in the analysis to respect the intention-to-treat principle, and his or her data are collected until 30 days after surgery (the final follow-up).

No interim analysis was planned, therefore there is no prespecified early termination rules for the study due to efficacy or futility.

## **Statistic significance and software**

Hypothesis tests will be two – sided with a significance level of 0.05. No Type I error corrections were conducted for multiple tests which will be interpreted as exploratory results. Analyses will be performed using the R program(R Foundation for statistical computing platform) version 4.1.0 or higher.

## **Distribution of Subjects**

Based on all subjects randomized, the number and percentage of subjects who completed the study and withdrew early, as well as the number and percentage of subjects who withdrew early for various reasons, will be summarized if presented. Listing will be presented for the reasons for early termination. Subjects who signed the informed consent but were not randomized will be summarized with listing of reasons provided. Subject distribution flow chart will be presented.

## **Protocol Deviation**

Based on all the randomized subjects, major protocol deviation will be summarized (if there is any), and listing will be provided for all.

## **General Approach**

INORDINATE is designed to detect whether intraoperative administration of up

to 80 ppm NO can reduce PPCs from 30% to 20% in participants undergoing surgical procedures under general anaesthesia who have been infected with SARS-CoV-2 within 7 weeks. Hypothesis tests will be two – sided with a significance level of 0.05. Strength of evidence (e.g., confidence intervals around estimates) will be provided. Data will be screened for integrity prior to full analysis.

### **Baseline and intraoperative Characteristics**

Demographic, baseline, and intraoperative characteristics will be summarised using descriptive statistics and will be presented by treatment group. Categorical variables will be reported as counts and percentages. Percentages will be calculated according to the number of trial participants for whom data are available. Where values are missing, the denominator will be stated and no assumptions or imputations will be made. Continuous variables will be summarized in either means and standard deviation or medians and interquartile range, according to the distribution of the variables.

T-test or Wilcoxon rank sum test will be used for comparison of continuous data.  $\chi^2$  test or Fisher's exact test will be used for comparison of categorical data. Normality for continuous variables will be assessed via the Shapiro-Wilk normality test and visually using QQ-plots and residual plots. Appropriate variable transformation such as natural logarithm will be applied in case of non-normality. Should normality not be obtained through transformation of the

data, alternative non-parametric methods (such as Wilcoxon rank sum test) will be applied. All statistical tests will be 2-tailed with  $p < 0.05$  considered statistically significant. All analyses will be performed on an intention-to-treat basis.

## **Blinded Analysis**

The primary analysis will be completed using blinded data. Treatment groups will be identified using coded identifiers (i.e. treatment A and B). Analyses will be performed and interpreted based on these blinded treatment groups, prior to unblinding.

## **Missing and outlier Data**

We anticipate no missing values in the primary outcome and very low missing values in other variables if any. The demographics and chronic medical history will be filled on site, intraoperative data will be monitored and recorded in the operating rooms, and the follow-ups until discharge of hospital or deaths can be traced back in the electronic health records. If patients are lost during the 30-day follow-ups, no imputation will be conducted for outcomes. Data missing at baseline will be reported as such. In case where low missing rate (<5%) occurred with no trace-backs available, multiple imputation will be performed as a sensitivity analysis.

Outliers will be subject to a confirmation request to the investigators. In

case of confirmation, their value will not be modified, and will be taken into account as it is during the analysis.

## **Presentation of Data**

The baseline demographic characteristics, surgical procedures performed will be summarized descriptively by treatment group.

Quantitative variables will be described using the following descriptive statistics: size, number of missing values, mean and standard deviation (SD), median and interquartile range (IQR), or minimum and maximum as appropriate depending on continuity.

Categorical variables will be summarized using the following descriptive statistics: number of people, number of missing values, frequencies, and percentages for each level of the variable (missing values will not be included in the denominator of the percentage calculation).

## **Computation of dates**

For calculation of durations, the date of index surgery corresponding to the date of randomization or admission to the intensive care unit will be considered as day 1, depending on the nature of the calculated duration. Therefore, the durations will be calculated from the following rule, for example for the postoperative length of hospital stay (in days):

$$\text{Date of discharge from hospital} - \text{date of index surgery} + 1$$

For the time interval between SARS-CoV-2 infection and surgery, it will be calculated in days as follow:

Date of index surgery - date of infection.

If only the infection date is reported as the first, middle or last third of the month, the day considered will be the 5th, 15th or 25th of the month.

## **Primary Analysis**

The effects of inhaled NO on incidence of PPCs will be reported as number and percentages and estimated with risk ratio and 95% confidence intervals calculated with Wald's likelihood ratio approximation test and with Chi-squared or Fisher's exact test for hypothesis testing. The unadjusted analysis will estimate risk ratios with 95% confidence intervals by two-by-two table with the use of log-Normal approximation. In addition, the effect size will be expressed as risk differences (95% confidence intervals) with the number needed to treat as the reciprocal of the risk difference, rounded to the nearest integer. This will further be analysed as the generalised linear models (GLM) under binomial family with either log or logit link where appropriate. Odds ratios or relative risks together with 95% confidence intervals will be reported. Further adjustment on stratification variables such as ARISCAT index and time interval from infection to surgery will be made. The point estimates with 95% confidence intervals will be reported.

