## **Randomization and Masking**

Eligible participants will be randomly allocated at 1:1 ratio to either NO inhalation or placebo. The randomization process will utilize permuted-block randomisation, with stratification based on the predicted risks of PPCs using the Assess Respiratory Risk in Surgical Patients in Catalonia (ARISCAT) index (< 45 [low and medium risk],  $\geq 45$  [high risk]), as well as the time interval from infection to surgery ( $\leq 10d$ , 11-28d, 29-49d). Random blocks of 4 or 6 will

be used for randomization. The allocation will be concealed by a web-based system that was accessed no earlier than the morning of the surgery.

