### Sample Size Consideration

The sample size for this study has been calculated based on the incidence of postoperative pulmonary complications of incidence of PPCs is reported to be approximately 20% for all surgical populations [62, 63] and increase up to 39.5% after COVID-19 infections[5]. The study assumes a 30% PPC incidence in the control group. We anticipate a 30% relative reduction (from 30% to 20%) in PPCs incidence for the iNO group. At 5% significance level and on consideration of 10% dropouts, the sample size needed to achieve 80% power is thus calculated to be 660 (330 per group) using a

two-sided Chi-squared test with continuity correction.

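### The deciding test for the primary endpoint ignores the six randomisation strata, and the SAP leaves its continuity correction open

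*SAP*

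**What the plan says.** - **Randomization and Masking:** "The randomization process will utilize permuted-block randomisation, with stratification based on the predicted risks of PPCs", measured by ARISCAT (below 45, or 45 and above), and also on the interval from infection to surgery (up to 10, 11–28 or 29–49 days). That makes 2 × 3 = 6 strata.
- **Primary Analysis:** the effect on PPCs is estimated as a risk ratio, "with Chi-squared or Fisher's exact test for hypothesis testing". A binomial GLM with log or logit link follows, and then: "Further adjustment on stratification variables such as ARISCAT index and time interval from infection to surgery will be made". The adjusted model yields point estimates with confidence intervals. It is not named as the source of the primary p-value.
- **Sample Size Consideration:** 660 patients (330 per group) for 80% power, using a "two-sided Chi-squared test with continuity correction".
- **Blinded Analysis:** the primary comparison is run on coded arms. "Analyses will be performed and interpreted based on these blinded treatment groups, prior to unblinding".

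**The concern.** There are two linked problems.

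First, the only test tied to the primary hypothesis pools over the factors used to balance the arms. Stratified allocation removes between-stratum variation from the treatment comparison, but a pooled two-by-two test still counts that variation as noise. Its true type I error then falls below 5% and some power is lost. The SAP itself treats ARISCAT as a predictor of this endpoint.

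Second, the form of the test is not fixed. Uncorrected chi-squared, corrected chi-squared and Fisher's test all fit the wording of the Primary Analysis section, and they can fall on different sides of 0.05. The sample-size section does not settle the matter, because it names the correction while its total fits the uncorrected formula.

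**Working it through.** **Inputs from the SAP.** Two-sided 5% level, 80% power, 10% dropout, "The study assumes a 30% PPC incidence in the control group", 20% on inhaled NO, 1:1 allocation, 330 per arm. Evaluable after dropout: 330 × 0.9 = 297 per arm (594 in total).

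**1. Reproducing 660.**

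n = [z₀.₉₇₅ √(2p̄q̄) + z₀.₈ √(p₁q₁ + p₂q₂)]² / (p₁ − p₂)², with p̄ = 0.25

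= [1.960 × √0.375 + 0.8416 × √0.37]² / 0.01 = 293.15, so 294 per arm.

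With correction: n′ = (n/4)[1 + √(1 + 4/(n × 0.10))]² = 312.8, so 313 per arm.

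| Formula | Evaluable per arm | Divided by 0.9 | Total |
|---|---|---|---|
| Uncorrected | 294 | 327 | 654 |
| Corrected | 313 | 348 | 696 |

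The stated 660 fits the uncorrected formula and not the corrected one that the text names.

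**2. What the open correction is worth.** Exact binomial enumeration at 297 per arm:

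| Test | Power, 30% vs 20% | Type I error at 30% |
|---|---|---|
| Chi-squared, uncorrected | 80.8% | 5.0% |
| Chi-squared, corrected | 77.9% | 4.1% |
| Fisher | 78.0% | 4.1% |

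Under the planned effect, the corrected and uncorrected tests disagree on significance in 80.8 − 77.9 = 2.9% of trials. An example is 89/297 versus 67/297:

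- Uncorrected: X² = 594 × (22 × 297)² / (156 × 438 × 297²) = 4.21, p = 0.040.
- Corrected: replace 22 × 297 by 22 × 297 − 297. Then X² = 3.83, p = 0.0502.
- Fisher: p = 0.0500, just above 0.05.

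**3. What stratification is worth.** The Cochran-Mantel-Haenszel (CMH) statistic is [Σ(aₕ − n₁ₕmₕ/Nₕ)]² / Σ{n₁ₕn₂ₕmₕ(Nₕ − mₕ)/[Nₕ²(Nₕ − 1)]}, summed over the six strata. Here aₕ is the events in one arm and mₕ the events in both.

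The SAP gives no stratum sizes or risks, so both are assumed. ARISCAT is split 65/35 and interval 20/40/40, giving strata of 77, 154, 154, 42, 83 and 84 patients. Overall control risk is 30%, and the risk ratio is 1.0 or 0.667. There were 100,000 simulated trials per scenario (Monte Carlo error about 0.1 point).

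| Assumed stratum control risks | all 30% | 22–45% | 16–57% | 10–74% |
|---|---|---|---|---|
| Outcome variance explained | 0% | 2.8% | 8.4% | 21.5% |
| Type I error: chi-squared, uncorrected | 5.0% | 4.7% | 4.1% | 2.8% |
| Type I error: chi-squared, corrected | 4.0% | 3.8% | 3.3% | 2.2% |
| Power: chi-squared, uncorrected | 80.6% | 81.0% | 81.7% | 83.1% |
| Power: CMH, uncorrected | 80.5% | 81.5% | 83.4% | 87.5% |
| Power: chi-squared, corrected | 77.8% | 78.2% | 79.0% | 80.4% |
| Power: CMH, corrected | 77.8% | 78.8% | 80.8% | 85.1% |

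Uncorrected CMH holds type I error at 5.0–5.2% throughout. Power forgone by not stratifying (both tests uncorrected) is 0, 0.5, 1.7 and 4.4 points. The mean standard error of the log risk ratio is 0.147 unadjusted, against 0.147, 0.145, 0.142 and 0.135 for Mantel-Haenszel, so the interval is 0%, 1%, 3% and 8% narrower.

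A second simulation (20,000 trials per scenario) used other assumed risks and a common odds ratio. CMH versus chi-squared power was 80.1% vs 80.2% with no stratum effect, 82.9% vs 81.6% with risks of 20–51%, and 90.2% vs 84.0% with risks of 9–72%. The direction is the same; the extreme case loses about 6 points.

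**The case against.** **The pooled test is valid, and stratum adjustment is already planned.** Both are true. The loss is in efficiency only, every non-zero figure for it rests on assumed stratum risks, and much of the gain in precision would appear in the planned adjusted estimates. What stays open is which p-value decides the trial. The adjusted model does not settle that: it leaves the link function open and may report either odds ratios or relative risks.

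**The power shortfall depends on dropout.** The SAP elsewhere expects little or no missing primary data. With all 330 per arm the corrected test has 82.4% power, and it reaches 80% at 312 per arm, so it falls short only if losses exceed about 5.5% (1 − 312/330). This stands as a limit on the shortfall. But 10% dropout is the plan's own design assumption, and the tests can still disagree near 0.05 at any sample size.

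**Fisher is unlikely to be needed.** The Secondary Analysis section chooses between the same two tests by incidence, and at 20–30% with about 300 per arm that would point to chi-squared. This is fair, but the primary section does not state the rule.

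**The change is late.** The SAP is dated 22-02-2024, about a year after the trial began on 17 February 2023. Dropping a named correction raises actual type I error from about 4% to the nominal 5%. This is the strongest objection. It calls for a dated amendment made without sight of results by arm and for deference to the published protocol. It does not justify leaving the test undefined.

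**Conclusion.** The concern holds. The primary hypothesis test is unstratified despite six randomisation strata, and the SAP does not say whether it is continuity-corrected or when Fisher's test would replace it.

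Validity is not at risk: there is no false-positive inflation, and the uncorrected test has its planned power. The correction costs about 3 points of power at 297 per arm (80.8% to 77.9%), which leaves it about 2 points below target; this uses only the SAP's own inputs. Not stratifying probably costs 0 to about 2 points, and 4 to 6 only if the strata are very prognostic; this rests on assumed stratum sizes and risks. When the strata carry no information, stratifying costs essentially nothing. The effect is modest, but it is worth correcting because the remedy is short and removes a choice that could decide a borderline result.

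**What to change.** In **Primary Analysis**:

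- Make the primary test a two-sided Cochran-Mantel-Haenszel test at 0.05 over the six randomisation strata (ARISCAT <45 or ≥45, by ≤10, 11–28 or 29–49 days), and state that no continuity correction is used.
- Make the Mantel-Haenszel risk ratio and risk difference, with 95% confidence intervals, the primary estimates.
- Label the unadjusted two-by-two results, the chi-squared or Fisher test, and all GLM risk ratios and odds ratios as supportive.

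In **Sample Size Consideration**, describe the calculation as uncorrected, which is what 660 fits.

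The cost is a few sentences. Stratum values are known at randomisation and no new data are needed. The drawback is a change of primary test after accrual began, so it should be a dated amendment made before the coded A/B analysis is run. Check it first against the published protocol, which was not available here. If that protocol fixes the unstratified test, keep that test as primary and state that it is uncorrected.
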